### Study Population

*Participant recruitment.* Participants will include 105 women aged 21-50. In order to achieve these enrollment goals, up to 260 adults could be recruited and screened for eligibility. Participants will be recruited primarily from the WisPIC outpatient mental health clinic where the PI maintains a clinical practice. We will also recruit through focused community networking with women's shelters and related service organizations and through community-wide general advertisements (e.g., newspaper ads, flyers, etc). We have worked with women's shelters in the past by contacting them to notify them of the study and providing brochures, which then they post in their facility. Interested participants would then contact us to learn more about the study.

*Inclusion/Exclusion Criteria.* Inclusion criteria will be 1) females age 21 – 50 years of age, 2) a current diagnosis of PTSD where the index traumatic event includes physical or sexual assault, 3) English speaking, and 4) medically healthy. Assault exposure will be defined as witnessed or directly experienced exposure to physical or sexual assault (Cisler et al. 2011; Kilpatrick et al. 2000; Kilpatrick et al. 2003; Resnick et al. 1993). To facilitate generalization to real-world populations of women with assault-related PTSD (Kessler et al. 1995; Kessler 2000), current comorbid major depressive disorder or anxiety disorders will not be exclusionary as long as the PTSD diagnosis is primary.

Exclusionary criteria include: 1) internal ferromagnetic objects (such as electronic devices, surgical implants, shrapnel, etc.), 2) major medical disorders (such as cancer), 3) ADHD, 4) psychotic disorders, 5) mental retardation, 6) developmental disorders, 7) active substance use disorders, 8) pregnancy, and 9) glaucoma. Medications will not be exclusionary, as long as the medication has been stable for at least 4 weeks and do not effect neurovascular properties upon which BOLD fMRI capitalizes (e.g., water pills). Acute sedatives / pain killers (e.g., benzodiazepines, vicodin) and prescription stimulants (e.g., Adderall) would not be permitted for 6 hours prior to the scan or for two hours after the scan. Medication prescription use will be modeled as a covariate. See below for detailed exclusion criteria.

Due to safety concerns, participants with these conditions will be ineligible to participate:

- Claustrophobia, or the inability to lie still in a confined space
- Major medical disorders (e.g., HIV, cancer)
- Magnetic metallic implants (such as screws, pins, shrapnel remnants, aneurysm clips, artificial heart valves, inner ear (cochlear) implants, artificial joints, and vascular stents), as these may heat, pull, or twist in the strong magnetic field of the MRI scanner
- Electronic or magnetic implants, such as pacemakers, as these may stop working
- Permanent makeup or tattoos with metallic dyes
- A positive pregnancy test (for females), since the effect of strong magnetic fields on the developing fetus remains unknown and inconclusive. (We will conduct a pregnancy test for all female participants of childbearing potential on the day of the MRI scan. Participants who test positive would be notified of this positive result)
- A self-reported history of loss of consciousness (greater than 10 minutes)
- Physical disabilities that prohibit task performance (such as blindness or deafness)

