**Version: 6**

**Date: 09/09/15**

**Page: 8**

*Digit span subscale of WAIS-IV:* measures working memory capacity.

*Spatial cueing task:* the spatial cueing task (e.g., Cisler et al., 2010) is a computer-administered protocol in which a stimulus picture (fear facial expression or neutral facial expression) is presented as a cue on either the left side of a computer screen, whose offset either predicts or does not predict the subsequent location of a response probe. There are 132 trials distributed evenly across the following factorial design: 2 (cue type: fear face vs neutral face) x 3 (cue position: opposite to probe, same as probe, center of screen). Each trial lasts 500 ms plus the participants reaction time.

*Reinforcement learning task:* The fear extinction protocol (see below) requires the tracking of associations between stimuli; thus, as a control for generic reinforcement learning, we would have participants complete a reinforcement learning task outside of the scanner. Similar to our other protocol (2016-1307), the task would resemble commonly used decision-making tasks towards the goal of earning as many points as possible. Participants select geometric shapes that are associated with a pre-determined probability of earning or losing points. Additionally, as a distractor, each of the shapes is associated with the appearance of a picture selected from the International Affective Picture System (IAPS), a well-normed and widely used set of pictures. Shapes would be associated with the occurrence of either a negative (e.g., snakes) or neutral (e.g., mountains) picture, as determined by the normed ratings of the IAPS. The points would displayed concurrently with the picture, but have no relationship to the amount of points earned. There would be ~150 trials and the task would take ~8 minutes to complete.

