**PI: [name].**

et al. 2006). In urn randomization, an algorithm modifies ongoing randomization probabilities based on prior composition of treatment groups, maximizing multivariate equivalence of treatment groups (Wei and Lachin 1988). Thus, urn randomization offers the benefits of balancing allocation of important prognostic variables in treatment groups while still retaining the benefits of random assignment (Stout et al. 1994). Participants will be randomized based on comorbid diagnoses, age, and current medication usage.

*Implementation.* The “urn” randomization will be implemented by a department statistician, who will have no direct contact with the participants and no knowledge of the pill assignment to the group labels and thus has negligible chance of biasing the randomization sequence or implementation.

*Blind Assessors.* The clinical research coordinators performing the assessments will be blind to the treatment conditions; thus minimizing the possibility of systematically biasing the assessment procedures.

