### Data analysis.

*Primary Analytic Framework for Fear Extinction Effects.* The overall data analysis framework for Aim 1 fear extinction analyses consists of a 3 (group: placebo vs 100 mg L-DOPA vs 200 mg L-DOPA) x 2 (cue: CS+ vs CS-) x 2 (context: A [learning context] vs B [extinction context]) x 6 (dopamine gene score: 0 [low endogenous dopamine] – 5 [high endogenous dopamine]) mixed design focused on Day 2 fear responding. Preliminary analyses would test for any baseline

differences in fear responding or extinction learning on Day 1 and include these variables as covariates if needed. Analyses would also control for ancestry as well as other demographic or clinical variables should they differ between groups.

*Neural circuit ROI definition and extraction.* The neural circuit indices would be 6 *a priori* regions of interest (ROI) with anatomical coordinates defined from the recent literature (Delgado et al. 2008; Haaker, Gaburro, Sah, Gartmann, Lonsdorf, Meier, Singewald, Pape, Morellini, & Kalisch 2013a; Milad, Wright, Orr, Pitman, Quirk, & Rauch 2007; Phelps, Delgado, Nearing, & LeDoux 2004; Schiller et al. 2008) and include bilateral amygdala, bilateral hippocampus, ventromedial PFC, dorsal anterior cingulate cortex. Following standard preprocessing, first-level analyses conducted for each individual separately would consist of whole-brain GLMs, in which the task design (CS+ vs CS- during Context A vs B) is modeled as boxcar events convolved with a canonical HRF. The task design is regressed onto each voxel's timecourse within a GLM framework and using restricted maximum likelihood to account for serial correlation, resulting in a whole-brain spatial map indicating the degree to which each voxel responds to CS+ vs CS- during Context A vs B. The mean contrast values for CS+ vs CS- as a function of context is then extracted from the voxels within 6 mm spherical ROIs for the six ROIs. These analyses would provide six (for each ROI) indices of activation, calculated separately for each participant, that would be used in multivariate analysis of variance (MANOVA) analyses to define the impact of L-DOPA and dopamine gene score on consolidation of fear extinction learning.

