**Planned Fear Extinction Analyses:** We would conduct three sets of MANOVA analyses, one with the set of Day 2 neural circuit indices (amygdala, dorsal anterior cingulate cortex, caudate) as dependent variables, one with the set of Day 2 physiological indices (SCR, HR, HRV) as dependent variables, and one with the set of Day 2 verbal/self-report indices (anxiety, UCS expectation) as dependent variables. In these analyses, the mixed effects of L-DOPA group, dopamine gene score, cue, context, and the interactions are entered as factors explaining variance in the multivariate combination of the set of dependent variables. Interactions with context would demonstrate the effect of the manipulations on robustness to context renewal effects. Additionally, any factors that differ between groups, such as Day 1 fear responding, age, or comorbid diagnoses, would also be entered as covariates should the balanced "urn" randomization fail. Given the three sets of tests, FDR correction (Benjamini and Hochberg 1995) would be used to control for alpha inflation. If the multivariate analyses reveal significant between-group differences in our measures of neural, psychophysiological and/or verbal/self-report, they would be followed up with simple effect testing to identify the specific conditions and measures driving the larger multivariate effect. We would additionally test for linear and quadratic contrasts for the group comparisons in order to establish dose-dependent learning, and its gating by dopamine gene score, effects on these primary DVs. All analyses would be completed prior to breaking the blind in order to minimize bias.

*Defining dopaminergic resting-state functional connectivity (FC).* Following the prior studies cited above (Haaker, Gaburro, Sah, Gartmann, Lonsdorf, Meier, Singewald, Pape, Morellini, & Kalisch 2013a; Kelly, de, Di, Copland, Reiss, Klein, Castellanos, Milham, & McMahon 2009), we

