*Testing the effect of altered resting-state FC on fear extinction learning consolidation.* Following identification of regions where FC with the DC, VS, and SN/VTA differ as a function of the L-DOPA x gene score interaction, we would then test whether individual differences in FC within these clusters predict subsequent consolidation of fear extinction learning. That is, we would test whether the hypothesized intermediate mechanism (acute dopamine neurotransmission and downstream dopaminergic neural networks) is related to the ultimate mechanism of interest (fear extinction learning). Consolidation of fear extinction learning from Day 1 would again be tested using Day 2 fear expression indices in Context A and Context B (i.e., fear extinction learning recall test) using multimodal assessments (neural circuit indices, psychophysiological, and self-report). GLMs would be used in which the outcome variable is regressed simultaneously onto the FC cluster, L-DOPA group, dopamine gene score, cue, and context. This would be repeated for the separate fear expression indices, with FDR controlling for alpha inflation due to multiple comparisons. These analyses would identify the clusters of voxels whose FC with the VS, DC, and SN/VTA predict enhanced recall on Day 2.

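### Medication use is promised as a covariate without condition in Study Population, but no Section G model carries it, and the Aim 2 connectivity slope is the most exposed

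*Combined protocol and SAP*

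**What the plan says.** Four places bear on this.

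- **Section C, Study Population.** Medicated women may enrol: "Medications will not be exclusionary, as long as the medication has been stable for at least 4 weeks", subject to a limit on drugs that affect the BOLD signal. The same paragraph then states the covariate rule, with no condition attached: "Medication prescription use will be modeled as a covariate".
- **Section C, Balanced Randomization.** Medication is one of the urn factors: "Participants will be randomized based on comorbid diagnoses, age, and current medication usage".
- **Section G, Aim 1 and FC models.** The primary analytic framework says: "Analyses would also control for ancestry as well as other demographic or clinical variables should they differ between groups". The planned MANOVAs say that "any factors that differ between groups, such as Day 1 fear responding, age, or comorbid diagnoses, would also be entered as covariates", in the event that the urn fails. The whole-brain FC models add covariates of non-interest if the urn does not match the groups on demographic and clinical severity variables. None of the three names medication.
- **Section G, FC-to-recall models (Aim 2).** Here "the outcome variable is regressed simultaneously onto the FC cluster, L-DOPA group, dopamine gene score, cue, and context". There is no covariate clause.

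The documents do not define what counts as a difference between groups or a failure of the urn, and they do not say how medication is coded.

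**The concern.** An analyst working from Study Population would put medication in every model. An analyst working from Section G would put it in only if the arms differed, and in the FC-to-recall model not at all. Because the urn is built to balance medication across arms, a rule triggered by arm differences would seldom admit it.

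Arm balance protects the randomised comparison. It does not protect terms that are measured and not assigned. FC is measured on Day 1 after the pill, and the gene score is inherited; the urn balances medication over neither. If a medication alters resting connectivity and also alters Day 2 heart rate, skin conductance or anxiety, FC and recall will be associated without any dopaminergic mechanism. The FC-to-recall model could then report that association as support for Aim 2.

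For the randomised comparison the stake is smaller. Leaving out a balancing factor leaves its variance in the error term, which makes the test slightly conservative and costs some power. The undefined trigger also leaves the choice of covariates open until the data have been seen.

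**Working it through.** The plan states no figure for this point, so there is none to reproduce. From the documents: 35 women per arm, N = 105, three urn factors including medication. Assumed, because the documents are silent: share medicated, size of medication effects, two-sided alpha of 0.05, urn parameters, and a significance test as the meaning of a group difference.

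**1. How often would the Section G trigger admit medication?** Three-arm urn randomization was simulated with three binary factors, one starting ball per arm, and one ball added to each other arm after every assignment. There were 1,500 runs per setting, with a chi-square test of medication by arm.

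| Share medicated | Simple randomization | Urn, balls summed over factors | Urn, most imbalanced factor |
|---|---|---|---|
| 30% | 5.0% | 2.9% | 0.6% |
| 50% | 4.6% | 2.1% | 0.7% |
| 70% | 5.2% | 2.5% | 0.5% |

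At p < 0.05 the trigger fires in about 0.5-3% of trials; at p < 0.10, in about 3-6%. The mean gap between the highest and lowest arm was still 10-12 percentage points under the urn, so a descriptive criterion could fire more often.

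**2. Aim 2: false FC effect when medication is omitted.** Let medication (50% prevalence) shift both FC and the outcome by d within-group SDs, with no direct link between them. It adds d²/4 to each variance and d²/4 to their covariance, so the spurious correlation is

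r = (d²/4) / (1 + d²/4),

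and the test of the FC slope has noncentrality of about √105 × r / √(1 − r²).

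- d = 0.3: r = 0.0225/1.0225 = 0.022; noncentrality 0.23; rejection about 5.6%.
- d = 0.5: r = 0.0625/1.0625 = 0.059; noncentrality 0.60; rejection about 9%.
- d = 0.8: r = 0.16/1.16 = 0.138; noncentrality 1.43; rejection about 29%.

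Simulation with arm terms in the model (10,000 replicates) agrees: 5.4%, 9.0% and 29.1% without the medication term, against 4.9%, 4.4% and 5.1% with it. This is one outcome per woman, before FDR, with gene score, cue and context left out.

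**3. Aim 1: size.** With medication simulated under the urn and left out of a 2-df group test on one outcome, size is about 4.4-5% if medication explains 5-10% of outcome variance, and about 4% if it explains 20%.

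**4. Aim 1: power.** For the same test, noncentrality is f² × 105 / (1 − R²), where R² is the variance share that adjustment removes. With f = 0.30 (assumed), f² × 105 = 0.09 × 105 = 9.45.

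| R² of medication | Noncentrality, adjusted | Power, adjusted | Power, unadjusted | Gain (points) |
|---|---|---|---|---|
| 5% | 9.45/0.95 = 9.95 | 0.801 | 0.779 | 2.2 |
| 10% | 9.45/0.90 = 10.50 | 0.823 | 0.779 | 4.4 |
| 20% | 9.45/0.80 = 11.81 | 0.868 | 0.779 | 8.9 |

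**The case against.** The strongest reply is that the two rules can be read together. Study Population fixes medication as a covariate; the Section G clauses then add further variables if the arms differ, and none of them says that nothing else may enter. Section G's lists are also not complete: control for ancestry appears in the primary framework and is not repeated in the later models. This stands. A reader might infer a flat contradiction that yields opposite models; the text supports only that a stated covariate is not carried into the model specifications.

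A reader might also infer a marked loss of size in Aim 1. If medication were exactly balanced within arm, unadjusted size would fall to about 3.8% at R² = 10% and 2.2-2.3% at 20%. The plan describes a probabilistic urn over three factors, not exact balance, so those figures do not apply and the loss in step 3 is the relevant one.

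The Aim 1 figures concern a group main effect, whereas the hypothesis is L-DOPA by gene score, with cue and context varying within each woman. The neural outcomes are CS+ versus CS− contrasts, from which a general medication shift cancels, and a medication main effect leaves cue and context interactions unchanged. This stands as a limit on those figures.

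For Aim 2 the objection is that the harm depends on the assumed shifts: at 0.3 SD it is negligible, and 29% needs 0.8 SD on both variables. That is correct, and the documents offer no figure to narrow the range. It does not answer the structural point that arm balance gives the FC slope no protection.

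Finally, a reader might extend the point to the reinforcement learning task, collected "as a control for generic reinforcement learning, we would have participants complete a reinforcement learning task outside of the scanner". The documents do not support this. They promise no covariate there, they do not place the task before the pill, and dopamine genes may act on fear partly through learning ability, so adjusting for it is a debatable modelling choice.

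**Conclusion.** The point holds as a gap between a stated commitment and the models meant to honour it. Study Population says medication will be modelled; Section G names it nowhere, and its balance-based trigger, read as a significance test at 0.05, would admit it in about 0.5-3% of trials.

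The consequence that matters is in Aim 2, where false-positive rates for the FC slope run from near nominal to about 29% over assumed shifts of 0.3 to 0.8 SD on both FC and outcome. These are conditional illustrations, not estimates for this trial. In Aim 1 the effect on size is small and in the conservative direction. The power cost for a simplified group test is about 2-4 points at R² of 5-10% and about 9 at 20%. Neither Aim 1 figure covers the L-DOPA by gene score interaction or the cue and context interactions. The correction should be made before analysis, while covariate choice cannot be influenced by results.

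**What to change.** State one rule in Section G that matches Study Population. Current medication use, with a pre-specified coding that matches the urn factor, enters every between-subject model: the primary framework, the three MANOVAs, the whole-brain FC models and the FC-to-recall models. It enters whatever the observed arm balance, and the clause on urn failure does not govern it. Name it explicitly in the FC-to-recall regressor list, where it matters most. The coding has to be written down, since the documents give none at present. Leave the reinforcement learning score out of this change.

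The cost is wording, plus one error degree of freedom for a binary factor or a few if medication classes are coded separately. If gene score is a six-level factor crossed with three arms, as written, 105 − 18 = 87 error degrees of freedom remain before the term is added. No new data collection is needed, as medications are already recorded on the data collection form.

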**PI: [name].**

- Psychotic disorders (e.g., schizophrenia)
- Any other condition that the investigator believes might put the participant at risk

Due to their effects on image quality, participants with the following MAY be ineligible to participate per Principal Investigator's judgment:

- Medications which may affect image quality (e.g., water pills)
- Nonremovable dental implants, such as braces or upper permanent retainers, as these will distort the MRI images we collect (note: fillings, crowns, and silver or gold teeth are OK)
- Any other condition, medication, or implant that the investigator believes would degrade image quality or render data unusable

*Phone screening.*

Initial assessment will occur in two phases. First, a phone screening will be conducted to ensure a high probability that participants are eligible for the study. The phone screening begins with a description of the study and phone screening and obtaining verbal consent to continue with the phone screen. This phone screening will assess the presence of assault exposure, PTSD symptoms, and transportation capability to WISPIC. The phone screening will also assess other possible exclusionary criteria such as medical disorders, internal metal, nonremovable dental implants, permanent makeup or tattoos with metallic dyes, history of loss of consciousness, claustrophobia, and any other conditions the investigator believes might put the participant at risk. If the participant meets probable inclusion criteria, the research coordinator will schedule the participant for phase-two of the assessment process. For clinic participants, this phone screening might be done in person.

*Informed Consent Process.* The participant will first be given a written and verbal description of the study and informed consent. The PI or designated staff will discuss the informed consent form with the subject volunteer. The consent process will take place in a quiet and private room. Subjects may take as much time as needed to make a decision about their trial participation and may take the document home if desired. The person obtaining consent will thoroughly explain each element of the document and outline the risks and benefits, alternate treatment(s), and follow-up requirements of the study. Participation privacy will be maintained and questions regarding participation will be answered. No coercion or undue influence will be used in the consent process. No research related procedures will be performed prior to obtaining informed consent. All signatures and dates will be obtained. A copy of the signed consent will be given to the participant. The informed consent process will be documented in each subject's research record.

*Participant assessment.*

Participants will complete several interviews, questionnaires, and neurocognitive tests to determine psychological and medical history, current life functioning, history of drug use, stress

experiences, individual traits, family functioning, and demographic variables. The first visit will be ~3-4 hours, during which they will complete the bulk of these measures and all interviews. Based on time, some of the questionnaires will be administered after the second MRI.

We hope to recruit participants from this study to participate in additional studies in our lab. To reduce overall burden on the participants, we would like to be able to use some of these participants' assessment data from this study for the new study (2017-0736). We will include a line in the informed consent document describing this use of the participant's data from this study and allowing the participant to provide informed consent to use their data for the additional study. All self-report and neurocognitive measures would be shared between the two studies. Structured clinical interview data would also be shared between the two studies, with the exception of the Clinician Administered PTSD Scale (CAPS), which will be re-administered in the new study to assess for current PTSD symptoms. If there is sufficient blood and saliva left over that could be shared with the other study as well, if not new blood / saliva samples would be collected. Participants who do not wish to have their data used from the current study would undergo all new assessments if they participate in the new study.

Structured clinical interviews:

*Structured Clinical Interview for DSM-IV Axis I Disorders (SCID-I):* measures current psychological functioning and drug use history (First et al., 2002).

*Structured Clinical Interview for DSM-IV Axis II Personality Disorders (SCID-II) Borderline Personality Disorder Module:* measures prevalence of symptoms related to the presence of borderline personality disorder (First et al., 2002).

*Clinician Administered PTSD Scale (CAPS):* Is the gold-standard structured interview to diagnosis PTSD and characterize symptom severity.

*National Women Survey Trauma Assessment (NSA):* assesses assaultive event exposure and other types of childhood adversity history and chronology (Kilpatrick, et al. 2000, Kilpatrick, et al. 2003; Resnick et al., 1993).

*Columbia Suicide Severity Rating Scale (CSSRS):* measures the severity of current suicidal ideation.

The structured clinical interview diagnostic assessments (SCID, CAPS) would be delivered by research staff and audiorecorded, with a random 20% selected for reliability checks. The clinical interviews are audiorecorded for the purpose of data quality assurance: we would conduct interrater reliability on randomly selected 20% of the interviews. The audiorecordings would be acquired with a digital recorder and the electronic files are stored according to participant ID (no identifying information) on a password protected computer that only study personnel have access to. After the interrater reliability has been assessed, we would delete the audiorecordings.

**Title:** Dopamine Enhancement of Fear Extinction Learning in PTSD (1R21MH108753)

